In the ruxolitinib-treated Phase III population, the overall frequency of AEs leading to study drug discontinuation was 11%. This frequency was similar across both studies. None of the AEs leading to discontinuation was reported in more than two patients in any group. In the ruxolitinib-treated Phase III population, the overall frequency of AEs requiring dose reduction

or interruption was 59.8%. This frequency was higher than in the control groups (placebo: 27.2%, BAT: 15.1%). The most frequently reported AEs requiring dose reduction or interruption in ruxolitinib treated patients were thrombocytopenia (36.9%), platelet count decrease (7.6%) and anemia (5.6%). The high frequency for thrombocytopenia is due to protocol-mandated dose reductions and interruptions. Although there were no protocol specified guidelines for dose reductions secondary to anemia, some investigators chose to reduce a patient's dose in the setting of anemia to minimize this particular cytopenia. The frequency of these AEs was higher than in the control groups. All other AEs requiring dose reduction or interruption occurred with a frequency of 1.3% or less in the ruxolitinib treated patients. There are no data from the use of ruxolitinib in pregnant women. Animal studies have shown that ruxolitinib is embryotoxic and foetotoxic. Teratogenicity was not observed in rats or rabbits; however, the exposure margins compared to the highest clinical dose were low and the results are therefore of limited relevance for humans. The potential risk for humans is unknown. As a precautionary measure, the use of ruxolitinib during pregnancy is contraindicated. Women of child-bearing potential should use effective contraception.

The most frequently reported adverse drug reactions were thrombocytopenia and anemia. Hematological adverse reactions (any Common Terminology Criteria for Adverse Events [CTCAE] Grade) included anemia (82.4%), thrombocytopenia (69.8%) and neutropenia (16.6%). Anemia, thrombocytopenia and neutropenia are dose related effects. The three most frequent non-hematological adverse reactions were bruising (21.6%), dizziness (15.3%) and headache (14.0%). The three most frequent non-hematological laboratory abnormalities were raised alanine aminotransferase (27.2%), raised aspartate aminotransferase (18.6%) and hypercholesterolemia (16.9%).

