Considering the typical hemoglobin level for many MF patients is already at the Grade 0/Grade 1 border (hemoglobin of 10 g/dL), assessment of a dose regimen that might provide clinically meaningful symptomatic and spleen size reduction benefits of ruxolitinib while lessening the degree of worsening hemoglobin levels is warranted.

Current label recommendation on starting doses in MF are 5, 15 or 20 mg BID, depending on platelet counts $50-100 \times 10^9/L$, $100-200 \times 10^9/L$ or $>200 \times 10^9/L$ respectively, regardless of hemoglobin level at baseline.

There is increasing literature suggesting the use of lower starting doses with up titrations depending on safety and efficacy in patients with anemia ([Tabarroki 2013](#), [Cervantes 2014](#), [Reilly 2014](#), [Harrison 2013](#), [Ho 2015](#)).

This multicenter phase II open label single arm study proposes to prospectively evaluate a starting dose of ruxolitinib 10 mg BID for 12 weeks with subsequent up titrations of 15mg BID and 20 mg BID in anemic myelofibrosis patients defined as a baseline hemoglobin < 10 g/dL (Please see [Figure 6-1](#) for details). The trial will evaluate if this alternative dosing approach achieves spleen reduction and symptom improvement to levels consistent with those reported in previous clinical trials but with an improved tolerability assessed by incidence of adverse events and transfusion requirements.

[figure not shown]
[figure not shown]

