6.2.3 Guidelines for dose escalations

Dose up titrations will be based on efficacy and platelet counts provided that ANC is $>500 \mu\text{L}$ and Hb level is $\geq 6.5 \text{ g/dL}$ as follows:

- A dose of 15 mg BID should be targeted in patients with platelet count $\geq 100 \times 10^9/\text{L}$ and $\leq 200 \times 10^9/\text{L}$ from week 12. This dose increase is optional for patients that achieved a $\geq 50\%$ reduction in spleen length at this visit relative to Baseline.
- A dose of 20 mg BID should be targeted in patients with platelet count $\geq 200 \times 10^9/\text{L}$ from week 16. This dose increase is optional for patients that achieved a $\geq 50\%$ reduction in spleen length at this visit relative to Baseline.
- Maximum dose allowed in the study is 25 mg BID and may be used from Week 20 in patients that did not achieve a 50% reduction in spleen length relative to Baseline and provided that platelet count is $\geq 200 \times 10^9/\text{L}$ at this visit.
- Patients who did not qualify for a dose increase at Week 12, may qualify for an increase at week 16 (from 10 mg BID to 15 mg BID). In that case, the Week 12 dose increase rules will apply. Similarly, patients who did not qualify for a dose increase at Week 16, may qualify for an increase later (from 15 mg BID to 20 mg BID). In that case, the Week 16 dose increase rules will apply.

Figure 6-1 Dosing Up-titration Diagram

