3. Its relationship to the study treatment (Reasonable possibility that AE is related: No, Yes) or its relationship to the study treatment (Reasonable possibility that AE is related: No, Yes, investigational treatment, Yes, the study treatment (non-investigational), Yes, both and/or indistinguishable)
4. Action taken with respect to study or investigational treatment (none, dose adjusted, temporarily interrupted, permanently discontinued, unknown, not applicable)
5. Whether medication or therapy taken (no concomitant medication/non-drug therapy, concomitant medication/non-drug therapy)
6. Outcome (not recovered/not resolved, recovered/resolved, recovering/resolving, recovered/resolved with sequelae, fatal, unknown)
7. Whether it is serious, where a serious adverse event (SAE) is defined as in [Section 8.2](#).

If the event worsens the event should be reported a second time in the CRF noting the start date when the event worsens in toxicity. For grade 3 and 4 adverse events only, if improvement to a lower grade is determined a new entry for this event should be reported in the CRF noting the start date when the event improved from having been Grade 3 or Grade 4.

All adverse events should be treated appropriately. If a concomitant medication or non-drug therapy is given, this action should be recorded on the Adverse Event CRF.

Once an adverse event is detected, it should be followed until its resolution or until it is judged to be permanent, and assessment should be made at each visit (or more frequently, if

necessary) of any changes in severity, the suspected relationship to the study treatment, the interventions required to treat it, and the outcome.

All patients who have AEs, whether considered associated with the use of the investigational product or not, must be monitored to determine the outcome. The clinical course of the AE will be followed up according to accepted standards of medical practice, even after the end of the period of observation, until a satisfactory explanation is found or the investigator considers it medically justifiable to terminate follow-up. Should the AE result in death, a full pathologist's report should be supplied if and when available.

SAEs must be reported as outlined in [Section 8.2.2](#). In addition, any SAEs which occur as a result of protocol specific diagnostic procedures or interventions must also be reported.

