4.8 Undesirable effects

Summary of the safety profile

The safety assessment was based on a total of 855 patients (with MF or PV) receiving Jakavi in phase 2 and 3 studies.

Myelofibrosis

In the randomised period of the two pivotal studies, COMFORT-I and COMFORT-II, the median duration of exposure to Jakavi was 10.8 months (range 0.3 to 23.5 months). The majority of patients (68.4%) were treated for at least 9 months. Of 301 patients, 111 (36.9%) had a baseline platelet count of between 100,000/mm³ and 200,000/mm³ and 190 (63.1%) had a baseline platelet count of >200,000/mm³.

In these clinical studies, discontinuation due to adverse events, regardless of causality, was observed in 11.3% of patients.

The most frequently reported adverse drug reactions were thrombocytopenia and anaemia.

Haematological adverse drug reactions (any Common Terminology Criteria for Adverse Events [CTCAE] grade) included anaemia (82.4%), thrombocytopenia (69.8%) and neutropenia (16.6%).

Anaemia, thrombocytopenia and neutropenia are dose-related effects.

The three most frequent non-haematological adverse drug reactions were bruising (21.3%), dizziness (15.3%) and headache (14.0%).

The three most frequent non-haematological laboratory abnormalities were raised alanine aminotransferase (27.2%), raised aspartate aminotransferase (19.9%) and hypercholesterolaemia (16.9%). In phase 3 clinical studies in MF, neither CTCAE grade 3 or 4 hypercholesterolaemia, raised aspartate aminotransferase nor CTCAE grade 4 raised alanine aminotransferase were observed.

Long-term safety: As expected with an extended follow-up period, the cumulative frequency of some adverse events increased in the evaluation of the 3-year follow-up safety data (median duration of exposure of 33.2 months in COMFORT-I and COMFORT-II for patients initially randomised to ruxolitinib) from 457 patients with myelofibrosis treated with ruxolitinib during the randomised and extension periods of the two pivotal phase 3 studies. This evaluation included data from patients that were initially randomised to ruxolitinib (N=301) and patients that received ruxolitinib after crossing over from control treatment arms (N=156). With these updated data, therapy discontinuation due to adverse events was observed in 17.1% of patients treated with ruxolitinib.

Polycythaemia vera

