For patients who did not take any drug, the cumulative dose is by definition equal to zero.

The actual cumulative dose is the sum of the non-zero doses recorded over the dosing period and the planned cumulative dose is the planned starting dose summed over the same dosing period.

Dose intensity and relative dose intensity

Dose intensity (DI) for patients with non-zero duration of exposure is defined as follows:

DI (mg / day) = Actual Cumulative dose (mg) / Duration of exposure to study treatment (day).

For patients who did not take any drug the DI is by definition equal to zero.

Planned dose intensity (PDI) is defined as follows:

PDI (mg / day) = Planned Cumulative dose (mg) / Duration of exposure (day).

Relative dose intensity (RDI) is defined as follows:

RDI = DI (mg / day) / PDI (mg / day).

DI and RDI will be summarized for Safety Set.

Dose reductions, interruptions or permanent discontinuations:

The number of subjects who have dose reductions, permanent discontinuations or interruptions, and the reasons, will be summarized for Safety Set.

‘Dose interrupted’, and ‘Dose permanently discontinued’ fields from the Dosage Administration CRF pages (DAR) will be used to determine the dose reductions, dose interruptions, and permanent discontinuations, respectively.

The corresponding fields ‘Reason for dose change/dose interrupted’ and ‘Reason for permanent discontinuation’ will be used to summarize the reasons.

A dose change is either ‘change in prescribed dose level’ or ‘dosing error’ where actual dose administered/total daily dose is different from the prescribed dose.

For the purpose of summarizing interruptions and reasons, in case multiple entries for interruption that are entered on consecutive days with different reasons will be counted as separate interruptions. However, if the reason is the same in this mentioned multiple entries on consecutive days, then it will be counted as one interruption.

Reduction: A dose change where the prescribed dose level is lower than the previous prescribed dose level or where the actual dose administered/total daily dose is lower than the calculated dose amount based on the prescribed dose. Therefore any dose change to correct a dosing error will not be considered a dose reduction. Only dose change is collected in the CRF, number of reductions will be derived programmatically based on the change and the direction of the change.

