2.8.1 Adverse events (AEs)

AE summaries will include all AEs occurring during on-treatment period. All AEs collected in the AE eCRF page will be listed along with the information collected on those AEs e.g. AE relationship to study drug, AE outcome etc. AEs starting during the post-treatment period will be flagged in the listings.

AEs will be summarized by number and percentage of subjects having at least one AE, having at least one AE in each primary system organ class (SOC) and for each preferred term (PT) using MedDRA coding. A subject with multiple occurrences of an AE will be counted only once in the respective AE category. A subject with multiple CTCAE grades for the same preferred term will be summarized under the maximum CTCAE grade recorded for the event. AE with missing CTCAE grade will be included in the 'All grades' column of the summary tables.

In AE summaries the primary system organ class will be presented alphabetically and the preferred terms will be sorted within primary SOC in descending frequency.

The following adverse event summaries will be produced by treatment; overview of adverse events and deaths (number and % of subjects who died), with any AE, any SAE, AEs by SOC and PT, summarized by relationship (all AEs and AEs related to study treatment), seriousness (SAEs and non-SAEs), leading to treatment discontinuation (drug withdrawn), leading to dose interruption/adjustment (dose increased or dose reduced), requiring additional therapy (concomitant medication or non-drug therapy) and leading to fatal outcome. In addition, a summary of serious and non-serious adverse events with number of occurrences will be produced (an occurrence is defined as >1 day between start and prior end date of record of same preferred term) as per EudraCT requirements.

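### SAP 2.8.1 puts adverse events that led to a dose increase in the same summary as those that led to a reduction or interruption; the two should be reported separately

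*SAP*

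**What the plan says.** SAP 2.8.1 lists the AE summaries to be produced by system organ class and preferred term. One covers events "leading to dose interruption/adjustment (dose increased or dose reduced", and no split by direction is planned.

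On data capture, Protocol 8.1.1 asks for each event: "Action taken with respect to study or investigational treatment (none, dose adjusted, temporarily interrupted, permanently discontinued, unknown, not applicable". Interruption has its own code; the dose-adjusted code carries no direction.

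Dosing is summarised separately in SAP 2.4.1: "The number of subjects who have dose reductions, permanent discontinuations or interruptions, and the reasons, will be summarized for Safety Set". Reductions there are derived from the dosing record using the direction of the change, so increases are kept out.

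Planned increases are governed by Protocol 6.2.3: "Dose up titrations will be based on efficacy and platelet counts", with floors for neutrophils and hemoglobin. The steps become available from Weeks 12, 16 and 20.

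Protocol 2.1 states the safety aim as "improved tolerability assessed by incidence of adverse events and transfusion requirements".

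**The concern.** In a trial where doses seldom rise, pooling the two directions would hardly matter. Here increases are part of the regimen. Protocol 8.1.1 counts worsening of a pre-existing sign or symptom as an adverse event, so a worsening disease symptom answered by a higher dose can be a valid AE record with a dose adjustment as its action. It would be counted beside thrombocytopenia that forced a reduction. The first points to too little effect, the second to too much toxicity.

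At stake is the reading of one descriptive safety table. The trial is single-arm and hopes to show better tolerability, and a table of AEs that forced the dose down or stopped it is one a reader will look for. As planned, no output gives that quantity by preferred term.

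**Working it through.** The plan gives no expected figure for this table, so there is none to reproduce. The check is of how the category is built.

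**1. Overall row.** Let A be the patients with at least one AE leading to reduction or interruption, and B those with at least one AE leading to an increase.

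- Pooled count = |A or B| = |A| + |B but not A|.
- Pooled rate − rate for A = |B but not A| / n.
- With the planned n = 50 (SAP 3), one such patient adds 1/50 = 2 percentage points.
- A patient with both kinds of event adds nothing. If there are no patients in B alone, the two rates are identical.

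The pooled rate can therefore equal or exceed the rate for A but never fall below it. The documents give no value for |B but not A|.

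**2. What puts a patient in B.** Protocol 6.2.3 ties up-titration to spleen response and platelet count, not to adverse events. A patient stepped up on schedule with no AE recorded as the reason is not in B.

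**3. Preferred-term rows.** The same identity holds row by row. For terms that point one way the row is clear: thrombocytopenia is an unlikely reason for an increase when increases require adequate platelets. For terms that can be either disease or drug effect it is not. Fatigue is an example: Protocol 1.1 lists it as a constitutional symptom of myelofibrosis, and Protocol 1.2.1.2.3 lists it among adverse events on ruxolitinib. A fatigue row that pools both directions cannot be interpreted.

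**4. Whether SAP 2.4.1 fills the gap.**

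| | SAP 2.8.1 table | SAP 2.4.1 summary |
|---|---|---|
| Source | AE records | Dosing records |
| Direction separated | No | Yes |
| By preferred term | Yes | No, by reason for the change |
| Limited to AEs | Yes | No; a reduction also includes a dose taken below the one prescribed |

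Neither output gives AEs leading to reduction or interruption by preferred term.

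**5. Whether direction is available.** The SAP wording presumes that it is. The action list in Protocol 8.1.1 does not show it. The eCRF is not among the documents, so it may or may not be captured on the AE form. The dosing record can supply it, since SAP 2.4.1 already derives direction there.

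**The case against.** The strongest case against is that little mixing should occur. Up-titration is scheduled and needs no adverse event; most of the table is by preferred term, so splenomegaly and thrombocytopenia would sit in different rows; SAP 2.4.1 already counts reductions and interruptions free of increases; and all AEs and all doses will be listed by patient. AEs leading to dose modification are not among the endpoints in Protocol Table 3-1. All of this stands, and it limits the point to the overall row and to terms that are both symptom and toxicity.

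A reader might go further and infer that in an up-titration trial the table must mix lack of effect with intolerance on a material scale. The documents do not support that: they give no count of AEs leading to an increase, and zero is consistent with them.

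A reader might also infer that pooling is what prevents comparison with the Phase III background, where "the overall frequency of AEs requiring dose reduction" or interruption is given as 59.8% (Protocol 1.2.1.2.3). That does not hold either. Neither document plans such a comparison. The Phase III patients were not selected for hemoglobin below 10 g/dL, started at 15 or 20 mg twice daily by platelet count, and had no protocol guidelines for reductions due to anemia, whereas this trial mandates interruption at low hemoglobin (Protocol 6.3.1.1). Those differences would remain after the table is split.

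A last fair objection concerns linkage. Matching AEs to dosing records by date alone could label a scheduled increase as caused by an AE that happened to coincide with it. The fix has to guard against this.

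**Conclusion.** The point holds as a minor one. SAP 2.8.1 pools dose increases with reductions and interruptions, so its overall rate is only an upper bound on AEs leading to reduction or interruption, and no other planned output gives that rate by preferred term. The excess is 2 percentage points for each patient whose only qualifying AE led to an increase, assuming 50 treated patients. The number of such patients cannot be estimated from the documents and may be zero, so no overall size is claimed. The conclusion assumes the table is programmed as written, with no split by direction in table shells that are not available here. The primary analysis and the listed endpoints are unaffected.

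**What to change.** In SAP 2.8.1, replace the pooled summary with two, each by system organ class and preferred term:

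- AEs leading to dose reduction or interruption;
- AEs leading to dose increase.

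State where direction comes from. Use the AE form if it is captured there. Otherwise take it from the Dosage Administration Record for AEs whose action is coded as a dose adjustment, under a matching rule fixed before database lock. The rule should set the date window between the AE and the dose change and should use the recorded reason for the change, so that a scheduled increase at Week 12, 16 or 20 coinciding with an AE is not counted as caused by it.

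The cost is one SAP line, one extra table and possibly one link between AE and dosing records. No new data collection is needed. If no AE led to an increase, the second table is empty and nothing is lost.

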2.8.1.1 Adverse events of special interest / grouping of AEs

An adverse event of special interest is a grouping of adverse events that are of scientific and medical concern specific to compound INC424. These groupings are defined using MedDRA terms, SMQs (standardized MedDRA queries), HGLTs (high level group terms), HLT (high level terms) and PTs (preferred terms). Customized SMQs (Novartis MedDRA queries, NMQ) may also be used. A NMQ is a customized group of search terms which defines a medical concept for which there is no official SMQ available or the available SMQ does not completely fit the need. It may include a combination of single terms and/or an existing SMQ, narrow or broad. For each specified AESI, number and percentage of patients with at least one event of the AESI occurring during on treatment period will be summarized.

A Case Retrieval Sheet (CRS; an Excel file) with the exact composition of the adverse events groupings is to be used to map reported adverse events to the AESIs groupings (termed Specific Event Categories (SECs) in the CRS). This file may be updated (i.e. it is a living document) based on review of accumulating trial data. The latest version of the CRS document available at the time of the analyses will be used.

A listing of all grouping levels down to the MedDRA preferred terms used to define each AESI will be generated.

2.8.2 Deaths

Separate summaries for on-treatment and all deaths (including post-treatment death) will be produced by treatment arm, system organ class, and preferred term.

All deaths will be listed for the Safety set, post-treatment deaths will be flagged. A separate listing of deaths prior to starting treatment will be provided for all screened subjects.

2.8.3 Laboratory data

The summaries will include all assessments available for the lab parameter collected no later than 30 days after the last study treatment administration date (see Section 2.1.1.3).

The following summaries will be produced for hematology and biochemistry laboratory data (by laboratory parameter):

- Changes from baseline in hematology/biochemistry parameters over time.
- Worst post-baseline CTC grade (regardless of the baseline status). Each subject will be counted only for the worst grade observed post-baseline.
- Shift tables using CTC grades to compare baseline to the worst on-treatment value
- .
- Trends of lab parameter values over time (baseline and selected on-treatment timepoints) should be displayed via boxplots based on time windows and corresponding tables displaying the statistics used for the box plots by the selected time points.

The following listings will be produced for the laboratory data:

- Listings of all laboratory data, with CTC grade and classification relative to the laboratory normal range. Lab data collected during the post-treatment period will be flagged.
- Listing of all CTC grade 3 or 4 laboratory toxicities

Liver function parameters

Liver function parameters of interest are total bilirubin (TBIL), ALT, AST and alkaline phosphatase (ALP).

The number (%) of subjects with worst post-baseline values will be summarized:

- ALT or AST > 3xULN
- ALT or AST > 5xULN
- ALT or AST > 8xULN
- ALT or AST > 10xULN
- ALT or AST > 20xULN
- TBL > 2xULN
- TBL > 3xULN
- ALT or AST > 3xULN & TBIL > 2xULN
- ALT or AST > 3xULN & TBIL > 2xULN & ALP < 2xULN (potential Hy's law)

Potential Hy's Law events are defined as those patients with a concurrent occurrence of AST or ALT > 3xULN and TBIL > 2xULN and ALP < 2xULN in the same assessment sample during the on-treatment period. Further medical review has to be conducted to assess potential confounding factors such as, liver metastases, liver function at baseline etc.

